15 ANALYTICAL PLAN

15.1 OUTCOME MEASURES

There is no generally accepted definition of clinically significant improvement in the treatment of methamphetamine dependency. The primary and secondary outcome measures are intended to explore various aspects of response to therapy and to help define a clinically meaningful response. The secondary measures add a measure of clinical relevance to the reduction of use by exploring the effect of therapy on psychosocial aspects of methamphetamine dependency. It is the intention of NIDA to use the data from clinical trials studying pharmacotherapies to treat methamphetamine dependence to develop an algorithm for combining self-report of use with urine methamphetamine assays to utilize both outcome measures to establish each day on study as a use-day or non-use day.

15.1.1 Primary Outcome Measure

The primary outcome variable for each subject is the weekly proportion of methamphetamine—free urine samples. Three urine collection days are scheduled per calendar week. The weekly methamphetamine-free sample is recorded as '0' if all three urine samples in the week were negative (< 300 ng/ml). The weekly methamphetamine-free sample is recorded as '1' if the proportion of weekly methamphetamine-free samples is between 0.67 and 0.75, inclusive. The weekly methamphetamine-free sample is recorded as '2' if the proportion of weekly methamphetamine-free samples is between 0.33 and 0.5, inclusive. The weekly methamphetamine-free sample is recorded as '3' if the proportion of weekly methamphetamine-free samples is 0.

Data from previous methamphetamine pharmacokinetic studies and other outpatient studies will be used to develop rules/algorithm for determining new versus old (carry over) use utilizing urine methamphetamine levels. The data generated in this study will be used with the algorithm, if developed, to determine new use versus carryover analyses.

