12.6 PREVENTION OF STUDY DROP-OUTS

Subjects will be encouraged to come for treatment and for the evaluation sessions as described in this protocol. To minimize missed sessions, they will be reimbursed for transportation and time spent in completing study assessments. It will be emphasized to subjects during screening that even if they have a relapse they should come to all scheduled appointments. They will be discouraged from using methamphetamine, but there will be no penalty for relapsing or for missed sessions.

Subjects will be encouraged to complete study visits, assessments, and CBT sessions, even if they are unable to tolerate the study medication. If a subject decides to drop out of the study prior to week 8, s/he will be asked to complete all final assessments (termination) at the time of drop out. If a subject wishes to stop taking the study agent but to continue to participate in and CBT sessions, s/he will continue to have all scheduled assessments according to the protocol and will complete the study at week 8. In this case, all study measures will be completed per protocol with the exception of those strictly related to the study agent.

A subject will be considered a drop out, if the subject misses six consecutive sessions during the 8 weeks of treatment. However, s/he will be asked to complete all termination assessments at the time of drop out and will be compensated for completing these assessments.

Subjects are free to discontinue the study and to refuse to participate in any of the procedures. If a subject drops out without making their intentions known, staff will attempt to contact them by telephone or written correspondence. Once the subject has been contacted and expresses their decision to discontinue from further participation in the study, the research staff will cease to try to make further contact.

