16.3 DATA ENTRY, PROCESSING AND ANALYSES

Data will be collected at the study sites on source documents that will be entered into eCRFs. When the study is completed and all data have been entered into the clinical database and the database has been checked by Quality Assurance and is locked, statistical analysis of the data will be performed by the data coordinating center's statisticians in accordance with the analytical plan section of this protocol. Periodically, during the investigation, data sets will be submitted to the NIDA DTR&D central data repository according to procedures specified in the study operations manual.

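### The 0–3 weekly score behind the primary outcome has no value for all-negative weeks of one, two or four samples, while all-positive weeks of any size score 3

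*Protocol*

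**What the plan says.** Protocol section 15.1.1 introduces the primary outcome as a proportion: "The primary outcome variable for each subject is the weekly proportion of" methamphetamine-free urines. It adds: "Three urine collection days are scheduled per calendar week". It then converts each week to a score from 0 (best) to 3 (worst):

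- Score 0 is a count. It is given "if all three urine samples in the week were negative", with negative meaning below 300 ng/mL.
- Score 1 is a proportion that "is between 0.67 and 0.75, inclusive".
- Score 2 is a proportion that "is between 0.33 and 0.5, inclusive".
- Score 3 is a proportion of 0, with no condition on the number of samples.

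Section 15.4.1 analyses this score with GEE for an ordinal response. Section 16.3 says the analysis will be done "in accordance with the analytical plan section of this protocol".

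The protocol expects incomplete collection. Sections 8.6 and 15.3 accept a subject as evaluable with four usable on-study urines, out of 8 × 3 = 24 scheduled. Section 12.6 says: "A subject will be considered a drop out, if the subject misses six consecutive sessions during the 8 weeks of treatment". Section 15.4.4 will compare the number of missing observations between arms. No section says how to score an all-negative week that does not contain exactly three samples.

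**The concern.** Three of the four categories rest on a proportion and one on a count. The two do not meet. A subject who attends two visits in a week gets a 3 if both samples are positive and a 2 if one is positive, but no score if both are negative. Whether the week has a score then depends on its result, even when the missed visit itself was pure chance.

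GEE copes with unequal numbers of observations per subject, as section 15.4.1 notes. It does not correct for weeks that go missing because of their outcome value. If such weeks are left out, or are not counted as clean, the primary outcome shifts towards use. The shift grows with the number of short weeks and with the share of negative samples. If attendance differs between arms, part of that shift can appear as a treatment difference.

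**Working it through.** **Step 1: reproduce the limits.** 1/3 = 0.33, 2/4 = 1/2 = 0.5, 2/3 = 0.67 and 3/4 = 0.75, to two decimals. Three samples can give only 0, 1/3, 2/3 or 1. The limits 0.5 and 0.75 therefore need weeks of two or four samples. This rules out two possible rescues: that only three-sample weeks are scored, and that the denominator is always three.

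**Step 2: apply the rule as written** to k negatives out of n samples, taking 2/3 as 0.67.

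| n | k = 0 | k = 1 | k = 2 | k = 3 | k = 4 |
|---|---|---|---|---|---|
| 1 | 3 | none | | | |
| 2 | 3 | 2 | none | | |
| 3 | 3 | 2 | 1 | 0 | |
| 4 | 3 | none | 2 | 1 | none |

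Among weeks of one or two samples, the only unscored ones are the all-negative ones. The 1-of-4 gap drops a mostly positive week and so works the other way, but missed visits cannot produce it.

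**Step 3: effect of short weeks.** The protocol gives neither attendance nor positivity rates, so both are assumed. Let a be the chance of attending each of three weekly visits and q the chance that a sample is negative, all independent. Unscored weeks are left out.

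For a = 0.8 and q = 0.5:

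- P(n = 1) = 3 × 0.8 × 0.2² = 0.096; P(n = 2) = 3 × 0.8² × 0.2 = 0.384; P(n = 3) = 0.8³ = 0.512. Together 0.992.
- Unscored: 0.096 × 0.5 + 0.384 × 0.25 = 0.144, and 0.144/0.992 = 14.5% of weeks with a sample.
- Sum of scores: n = 1 gives 0.048 × 3 = 0.144; n = 2 gives 0.096 × 3 + 0.192 × 2 = 0.672; n = 3 gives 0.512 × 1.5 = 0.768. Total 1.584.
- Mean as written: 1.584/(0.992 − 0.144) = 1.87. At full attendance it is 1.50.
- Mean if all-negative weeks of any size score 0: 1.584/0.992 = 1.60.

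The same calculation at 80% attendance for other assumed rates:

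| q | Unscored weeks | Mean, full attendance | Mean as written | Mean after fix |
|---|---|---|---|---|
| 0.3 | 6% | 2.10 | 2.33 | 2.18 |
| 0.5 | 15% | 1.50 | 1.87 | 1.60 |
| 0.7 | 26% | 0.90 | 1.32 | 0.98 |
| half 0.9, half 0.1 | 21% | 1.50 | 1.94 | 1.54 |

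**Step 4: a fully abstinent subject.** The share of attended weeks with no score is P(n = 1 or 2)/P(n ≥ 1). At 90% attendance this is (0.999 − 0.729)/0.999 = 27%. At 75% it is (0.984 − 0.422)/0.984 = 57%. An always-positive subject loses no attended week.

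**Step 5: unequal attendance with no true difference.** With q = 0.5 in both arms and attendance of 90% and 80%, the means as written are 1.69 and 1.87, a gap of 0.18. After the fix they are 1.56 and 1.60, a gap of 0.04. For scale, at full attendance moving q from 0.5 to 0.7 changes the mean by 1.50 − 0.90 = 0.60.

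**The case against.** The strongest reply is that the intent is clear. The outcome is named as a proportion, three of four categories use one, and two-sample weeks were foreseen, so an analyst would naturally score a proportion of 1 as 0. Section 15.4.1 also allows adjustments to the structure of the data. On that reading the asymmetry disappears. This is probably what was meant, but the text does not say it, and a general allowance for adjustments does not define these weeks. The choice would be left until data are in hand, although section 16.3 ties the analysis to this section. It is also not detail deferred to an analysis plan: the protocol writes a scoring rule, and the rule is incomplete.

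A reader might infer that the plan deletes abstinent weeks and keeps use weeks. The documents do not support that. No section says what happens to an unscored week, and all-negative weeks of three samples do score.

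The size is also open to challenge. Independent attendance tends to produce many part-weeks. Absence in long runs or drop-out mainly gives empty weeks, which have no proportion whatever the subject's true use. Section 12.4 lets visits move to adjacent days, and section 12.10 pays for each visit with a urine, which both work against short weeks. That is fair. The six-session drop-out rule is only partial evidence for short weeks: a run of five misses (3 + 2) empties one week and shortens one or two others.

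Finally, 0.67 is plainly 2/3 rounded and is not a defect of substance.

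**Conclusion.** The point holds as a defect in the written definition of the primary outcome. All-negative weeks of one, two or four samples, and the 1-of-4 week, have no score; all-positive weeks always score 3; nothing elsewhere in the protocol repairs this.

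A shift towards use follows only if unscored weeks are left out of the GEE or are not counted as clean. Its size is conditional on assumed rates. At 80% attendance with independent samples, 6% to 26% of weeks are unscored over the rates tried, and the mean score rises by between 0.23 (2.10 to 2.33) and 0.44 (1.50 to 1.94). The 27% and 57% losses apply to a fully abstinent subject and are an upper illustration, not an expected trial-wide figure. Bias between arms needs a difference in attendance, which the protocol gives no reason to expect or exclude. A reader might conclude that the trial's comparison is biased by a known amount; the protocol cannot show that. This is a pilot study, but the gap sits in its primary outcome and should be closed before analysis.

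**What to change.** In section 15.1.1, let p be the number of negative samples divided by the number obtained in the study week, for any week with at least one sample. Score 0 if p = 1; 1 if 0.5 < p < 1; 2 if 0 < p ≤ 0.5; 3 if p = 0.

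This scores every week that has a sample. It keeps the evident grouping of 1/3 and 1/2 as 2 and of 2/3 and 3/4 as 1, places 1/4 in score 2, and leaves the ordinal GEE unchanged.

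The cost is a wording change and a few lines of code, with no new data. There are two small downsides. One- and two-sample weeks carry less information than full weeks but count equally. A residual shift also remains because 1 of 2 scores 2: in the worked example 1.60 − 1.50 = 0.10, about a quarter of the 0.37 under the rule as written.

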15.1.2 Secondary Outcomes Measures

Effect on methamphetamine and other drug use during the 8 week treatment period

- B. Proportion of subjects with 3 consecutive weeks of abstinence as measured by 9 consecutive methamphetamine-free (<300 ng/ml) urine samples.
- C. Weekly mean proportion of methamphetamine non-use days based on subject's self report of use (SUR) during the 8-week treatment period.

- D. The proportion of subjects who decrease the overall proportion of methamphetamine use to 50% or less of their use in the month prior to the study based on timeline followback for the before study period and self report using the SUR during the on study period.
- E. The maximum number of consecutive methamphetamine non-use days by subject's self report of use (by SUR).
- F. The number of methamphetamine-free urines during the 8-week period.
- G. Weekly mean proportion of non-use days of other drug use, by other drug according to SUR including marijuana, nicotine, and alcohol.
- H. Number of negative urines for tetrahydrocannabinol, cocaine, amphetamines, barbiturates, opiates, and benzodiazepines, and negative alcohol breathalyzer tests.
- H. Log weekly median quantitative urine methamphetamine levels.
- I. Proportion of subjects who reduce overall median of methamphetamine quantitative urine concentration to 50% of his/her baseline values.
- J. Proportion of subjects who reduce the overall median of methamphetamine quantitative urine concentration to 25% of his/her baseline value.

Reduction in the severity of methamphetamine dependence, craving, and withdrawal

- K. CGI-O scores (dependence).
- L. CGI-S scores (dependence).
- M. ASI-Lite composite score of the drug section and methamphetamine use question individually (dependence) and composite scores of the other sections (other global measures of improvement).
- N. BSCS scores (craving)
- O. MAWQ scores (withdrawal)

Severity of Depression

P. HAM-D scores.

Changes in Cognitive Functions

Q. Change in cognitive function at study end compared to baseline.

Treatment Retention

R. Number of days in treatment.

Safety of Ondansetron

S. AEs, laboratory data, physical exams, ECG results, and vital signs.

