13.6.14 Timeline Followback

Detailed histories of methamphetamine and alcohol use over the past 30 days prior to screening will be obtained using the timeline followback method. The timeline followback method was described and validated by Sobell *et al.*, (1986) for reporting alcohol use. It has also been found to be a reliable method for assessing the history of psychoactive substance use in drug-abusing populations (Fals-Stewart *et al.*, 2000). In addition, this method will be applied to counting capsule usage reported by the subject for treatment compliance determinations.

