13.6.21 Substance Use Report (SUR)

The SUR includes the subject's report of use of methamphetamine, marijuana, nicotine, and alcohol use for each day of the week. The subject is asked to report any use during days since the last clinic visit and the current visit. The day that the subject is reporting use is not scored until the subsequent visit as use may occur later in the day.

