15.3 INTENT-TO-TREAT AND EVALUABLE SUBJECT POPULATIONS

The intent-to-treat population is defined as the subjects who are randomized and receive the first day's study agents. The evaluable population is defined as the subjects who are randomized, meet

all of the inclusion and exclusion criteria, and who contribute at least four (4) usable on-study urine samples and 21 days of self report of methamphetamine use/non-use by SUR.

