15.5 SAMPLE SIZE

There is no data to determine what type of effect ondansetron will have on the study population because this is a pilot study. Based on other clinical trials of drug abuse treatments, 30 evaluable subjects in study arms will give an indication of treatment effect. It was estimated that 30% of subjects will not meet the evaluable subject criteria, thus to obtain 30 evaluable subjects in each treatment arm, 45 subjects will need to be randomized to each arm for a total of 180 subjects randomized and enrolled on the study.

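### In the intent-to-treat analysis, responder outcome D has no minimum reporting period, so low- and moderate-frequency users who leave early with unchanged use can count as having halved it.

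*Protocol*

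**What the plan says.** Protocol Section 15.1.2 gives outcome D as "The proportion of subjects who decrease the overall proportion of methamphetamine use to 50% or less of their use in the month prior". Its stated sources are "timeline followback for the before study period and self report using the SUR during the on study period". Neither a minimum number of on-study days nor a rule for subjects who leave is attached.

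The two sides of the ratio are observed differently:

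- **Before study.** Section 13.6.14 collects "Detailed histories of methamphetamine and alcohol use over the past 30 days prior to screening", a fixed window.
- **On study.** Section 13.6.21 ties the SUR to attendance: "The subject is asked to report any use during days since the last clinic visit and the current visit". It adds: "The day that the subject is reporting use is not scored until the subsequent visit as use may occur later in the day". For someone who does not return, the record ends the day before the last attended visit.

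Section 15.4.1 requires every secondary efficacy outcome to be analysed in two populations, both defined in Section 15.3. For the first, "The intent-to-treat population is defined as the subjects who are randomized and receive the first day's study agents". The second is limited to eligible subjects "who contribute at least four (4) usable on-study urine samples and 21 days of self report of methamphetamine use/non-use by SUR". Section 15.4.1 also says that major differences between the two sets of results will be explored. Section 15.5 on sample size says: "It was estimated that 30% of subjects will not meet the evaluable subject criteria".

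**The concern.** A proportion over very few days is coarse. With 2 reported days and a baseline of 10 in 30, the only way to be at or below half the baseline rate is to report no use on both days, and a subject whose habit has not changed will often do that. With 56 days the same subject almost never passes. The threshold is therefore easiest to pass for those observed least.

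This sets D apart from its neighbours. Outcome B needs nine consecutive negative urines, and E and F are counts that leaving early can only limit. In D, leaving before a relapse is reported helps the subject succeed. If subjects leave one arm sooner than another, that arm gains false responders in the intent-to-treat comparison. Section 5.2 lists self-reported reduction from baseline among the measures of success, so the result would be read as evidence on efficacy and dose.

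**Working it through.** **The plan's own figure.** The protocol gives no number for D. The nearest stated figure is the inflation for non-evaluable subjects in Section 15.5: 30/(1 − 0.30) = 42.9, so 43 per arm. The stated 45 per arm is consistent with rounding up (45 × 0.70 = 31.5 evaluable).

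**Inputs.** From the documents: a 30-day baseline, up to 56 on-study days, a pass mark of 50% and a stratum boundary at 10 use days in 30. Assumed, because the protocol gives no distribution: baseline use days b, reported days k, unchanged true use, and independent days (relaxed below).

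On a Monday-Wednesday-Friday schedule with first dose on a Monday, and because the visit day is not scored, k = 2 means last seen on Wednesday of week 1. Likewise k = 4 means Friday of week 1, k = 7 Monday of week 2, and k = 14 Monday of week 3.

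**Formula.** With X ~ Binomial(k, b/30), a false responder has X/k ≤ 0.5 × b/30.

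Worked for b = 10 (rate 1/3, pass mark k/6):

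- k = 2: X = 0 only, (2/3)² = 0.444.
- k = 4: X = 0 only, (2/3)⁴ = 0.198.
- k = 7: X ≤ 1, (2/3)⁷ + 7(1/3)(2/3)⁶ = 0.059 + 0.205 = 0.263.
- k = 56: X ≤ 9, 0.003.

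The rise from 4 to 7 days occurs because one use day becomes allowable at k = 6.

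| Baseline | k = 2 | k = 7 | k = 14 | k = 21 | k = 56 |
|---|---|---|---|---|---|
| 6/30 | 0.64 | 0.21 | 0.20 | 0.18 | 0.02 |
| 10/30 | 0.44 | 0.26 | 0.11 | 0.046 | 0.003 |
| 15/30 | 0.25 | 0.06 | 0.03 | 0.013 | <0.001 |
| 20/30 | 0.11 | 0.045 | 0.004 | 0.002 | <0.001 |
| 25/30 | 0.03 | 0.002 | <0.001 | <0.001 | <0.001 |
| 30/30 | 0 | 0 | 0 | 0 | 0 |

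**Sensitivity.** If use days cluster (first-order Markov, lag-1 correlation 0.5), the values at k = 7 are 0.43, 0.40, 0.20, 0.16 and 0.05 for 6, 10, 15, 20 and 25 in 30. If the baseline count is itself random, the 10/30 row at k = 7 becomes 0.21 and at k = 14 stays at 0.11.

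**Effect on an arm.** Each 10 percentage points more subjects leaving at one week adds 0.10 × (0.263 − 0.003) = 2.6 points of false responders at 10/30, or 0.026 × 45 = 1.2 subjects per arm. At 20/30 it adds 0.10 × 0.045 = 0.45 points.

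**Other denominator.** Suppose D were read over all 56 days with nothing said about unreported ones. A subject who used on both of 2 reported days would score 2/56 = 3.6%, below the 16.7% pass mark for 10/30. That reading helps only if unreported days are given a value, and the protocol gives none.

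**The case against.** The case against is substantial.

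- **The denominator is not spelled out.** Section 15.1.2 does not say that only reported days count, and a statistical analysis plan not shown here may settle it. That tempers the point. However, Section 16.3 says the final analysis follows the protocol's analytical section, and the natural reading of an overall SUR proportion uses the days on the SUR.
- **The evaluable analysis has a floor.** This stands. A reader might infer that D has no minimum anywhere; the 21-day requirement and the promised exploration of differences do not support that. The defect is confined to intent-to-treat. Exploring a discrepancy still does not define a valid intent-to-treat result, and the evaluable set is selected on retention after randomization.
- **Leavers are followed up.** Sections 12.6 and 13.4 ask for termination assessments including an SUR, which recovers trailing days for those who return. Section 12.6 also lets a subject stop the agent and keep all scheduled assessments, so intolerance is not the same as leaving. Those who do not return remain affected.
- **The size depends on who is averaged.** This also stands. Over baselines of 5, 10, 15 and 20 in 30, the mean at k = 2 is (0.694 + 0.444 + 0.250 + 0.111)/4 = 37%. Adding 25 and 30 in 30 gives (1.499 + 0.028 + 0)/6 = 25%.
- **D is one of many secondary outcomes in a pilot** whose primary outcome is urine-based. This limits the consequence without making the definition sound.

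**Conclusion.** The point holds for the intent-to-treat analysis of D. Low- and moderate-frequency users who leave within about two weeks with unchanged use can be classed as having halved it. At 10/30 with independent days the probability is 44%, 26% and 11% at 2, 7 and 14 reported days, against 0.3% with full reporting. Clustering of use days raises these figures.

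Two stronger readings are not supported. One is that early leavers in general are often misclassified: at 20/30 the rate is about 4.5% at one week, and for daily users it is zero. The other is that the trial will show a particular bias between arms. The documents give neither the baseline use distribution nor the timing of leaving by arm, and the 30% in Section 15.5 covers every reason for being non-evaluable. What can be said is that the definition allows a result favouring the arm that subjects leave sooner, by roughly one subject in 45 for each 10-point difference in one-week leaving at 10/30.

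**What to change.** In Section 15.1.2, add one sentence: for the intent-to-treat analysis of D, a subject with fewer than 21 days of SUR data is a non-responder. This reuses the protocol's own floor and makes the false-responder rate zero below it. Some error remains just above the floor: at exactly 21 days it is 4.6% at 10/30 and 18% at 6/30 with independent days.

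Add one sensitivity analysis over days 1 to 56 with unreported days set to the subject's own baseline rate p. With x use days in k reported days, response then needs x + (56 − k)p ≤ 28p, that is x ≤ (k − 28)p. No one with fewer than 28 reported days can pass.

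The cost is a sentence and a table. The downside is small: some early leavers who were abstinent count as non-responders, so an arm with more leaving is now marked down instead of up.

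Counting every unreported day as use would be too harsh. A 5/30 subject could have only 4 use-or-unreported days of 56 (0.5 × 5/30 × 56 = 4.7), and D would become largely a retention measure, which outcome R already is. Nor should such a rule be carried to outcomes I and J, because a missing sample treated as use has no defined concentration to enter a median.
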